6.1.2. Assessment of Adverse Events

Each event recorded on the AE CRF will be assessed by the Investigator with regard to the following categories.

Severity

Severity of AEs will be graded as one of:

- **Mild:** Awareness of signs or symptoms but easily tolerated. A type of AE that is usually transient and may require only minimal treatment or therapeutic intervention. The event does not generally interfere with usual activities of daily living.
- **Moderate:** A type of AE that is usually alleviated with additional specific therapeutic intervention. The event interferes with usual activities of daily living, causing discomfort but poses no significant or permanent risk of harm to the research subject.
- **Severe:** Incapacitating the ability to do work or to do activities. A type of AE that interrupts usual activities of daily living, or significantly affects clinical status, or may require intensive therapeutic intervention

Relationship to Study Medication

The Investigator or designee, using clinical judgment, will assess the causality/relationship between each AE and the most recently administered study medication (i.e., whether there is a reasonable possibility that the drug caused the event) and record that assessment in the CRF.

Unrelated: The AE is clearly not related to the study medication. The AE is clearly explained by another cause, or exposure to the study medication has not occurred.

Related: The AE may be related to the study medication. The AE and administration of the study medication are considered reasonably related in time, but the AE is more likely explained by the study medication than another cause.

AE reporting will extend from randomization until completion of the Follow-Up Visit. AEs occurring after the end of the clinical trial must be reported if the Investigator considers there is a causal relationship with the study medication.

All AEs, regardless of the relationship to study medication, will be recorded in the CRF.

All reports should contain a brief description of the event, date of onset, date of resolution, severity, treatment required, relationship to study medication, outcome, and whether the event is classified as serious. Whenever possible, the Investigator should group signs or symptoms that constitute a single diagnosis into a single event term. For example, “cough, rhinitis, and sneezing” might be grouped together as “upper respiratory tract infection.”

A treatment-emergent clinically significant abnormal laboratory value should be recorded as an AE.

6.1.3. Reporting Serious Adverse Events

All SAEs that occur from time of informed consent until completion of the final visit, whether considered to be associated with the study medication or not, must be reported within 24 hours by telephone, e-mail or fax to the Sponsor's Medical Monitor and/or Sponsor's designee using the appropriate contact details provided. The minimum information required for an initial report is:

- Sender of report (name, address of Investigator)
- Subject identification (subject number, NOT subject name)
- Protocol number
- Description of SAE and date of onset
- Relationship assessment
- Date of visit and study visit number
- Current status of subject

However, whenever possible, all points on the SAE form should be completed and the form faxed or scanned and emailed to the Sponsor or designee. The site should also notify the Sponsor or designee by email or voicemail if the information was sent via facsimile. In addition, the event must be documented in the CRF.

After receipt of the initial report, the Sponsor's Medical Monitor or designee will review the information and, if necessary, contact the Investigator to obtain further information for assessment of the event. The Sponsor or designee will be responsible for all information processing and reporting according to local legal requirements.

The Sponsor or designee will determine the SAEs requiring expedited reporting to regulatory agencies. The clinical trial site personnel are responsible for reporting these events to their Ethics Committee in accordance with applicable laws and regulations.

6.1.4. Follow-up of Adverse Events

All AEs and SAEs experienced by a subject, irrespective of the suspected causality, will be monitored until the event has resolved, until any abnormal laboratory values have returned to baseline or stabilized at a level acceptable to the Investigator and Medical Monitor. Any SAE that occurs after final visit but is felt to be related to the study medication by the Investigator must be reported to Sponsor or designee and any necessary regulatory agencies and must be followed by the Investigator until resolution or stabilization.

6.2. Clinical Safety Laboratory Abnormalities

Blood and urine samples for routine safety laboratory parameters will be collected at timepoints specified in the Schedule of Events. The Investigator will document review of all labs and will determine and document clinical significance. All abnormal laboratory values that are clinically

significant, treatment-emergent, and meet one of the following conditions (as determined by the Investigator) should be recorded as a single AE:

- Accompanied by clinical symptoms, or
- Requires a change in concomitant therapy

6.3. ECG Abnormalities

Any clinically significant ECG abnormality will require evaluation by the Investigator in consultation with the Sponsor's Medical Monitor to determine if the abnormality is significant and whether it is safe for the subject to continue in the study.

6.4. Pregnancy

Female subjects who become pregnant during the study period must be discontinued from the study. Pregnancy in a study subject should be reported by the Investigator within 1 business day to the Sponsor's Medical Monitor. Pregnancy in itself is not regarded as an AE unless there is a suspicion that an investigational product may have interfered with the effectiveness of a contraceptive medication.

Any female subject or partner of a male study subject who becomes pregnant during the trial will be asked to agree to regular reporting of the progress and outcome of her pregnancy to the Investigator (or designee) and Sponsor. Monitoring of the pregnant subject or partner should continue until the outcome (spontaneous miscarriage, elective termination, normal birth or congenital abnormality) of the pregnancy is known and documented even if the subject was discontinued from the study.

All reports of congenital abnormalities/birth defects are SAEs. Spontaneous miscarriages should also be reported and handled as SAEs. Elective abortions without complications should not be handled as AEs.

7. STUDY MEDICATION

7.1. Study Medication

CST-103 is provided as 40 µg capsules and matching placebo. CST-107 is provided as 1 mg capsules and matching placebo. Additional details on the study medication can be found in the [Investigator Brochure](#).

7.2. Study Medication Dosing and Administration

Study treatments are:

- CST-103/CST-107 PO taken in the morning after the first meal of the day during each Treatment Period:
 - 80 µg CST-103, administered as two 40 µg capsules QD Day 1 – Day 14

- 1 mg CST-107, administered as one 1 mg capsule QD Day 1 – Day 14
- Matching placebo taken daily during each Treatment Period

7.2.1. Randomization

The designated Interactive Response System (IRT) will be used to randomize subjects into the study on the first day of the Lead-In Period. Eligible subjects will be randomly assigned in a 1:1 ratio to one of the following two treatment sequences (CST-103/CST-107 to placebo or placebo to CST-103/CST-107). The IWRS will provide the randomization number.

Randomization will be stratified by the following factors:

- Disease criteria:
 - Cohort A: RBD+PD or MCI
 - Cohort B: DLB or PDD
- Sex (Male vs Female)

7.2.2. Blinding

This clinical trial is a double-blinded study, with the Sponsor, subjects, and site personnel (e.g., study nurses, coordinators, investigators) blinded to treatment assignment. Limited staff will have access to treatment assignments, such as the unblinded statistical team, IRT system administration, and drug supply management team. Limited CuraSen staff or designees who are not otherwise involved in study conduct may be unblinded during study to evaluate accruing data.

A subject's treatment assignment should only be unblinded by the PI and/or by CuraSen's Medical Monitor when knowledge of the treatment is essential for the further management of the subject or may impact the safety of subjects currently enrolled. Unblinding for any other reason will be considered a protocol violation. The PI is strongly encouraged to contact the CuraSen Medical Monitor before unblinding any subject's treatment assignment, but must do so within 1 working day after the event and must document the unblinding in the subject's source records.

CST-103 40 µg-matched placebo and CST-107 1 mg-matched placebo will be packaged and color-, size-, and shape-matched to be indistinguishable from CST-103 40 µg and CST-107 1 mg.

7.2.3. Packaging and Labeling

All study medication to be used in this study will be packaged in bottles of 30 capsules each. The clinical label will identify the product by name, lot number, Sponsor, storage conditions and expiration dating period. The products are limited to investigational use only.

7.2.4. Storage and Handling

Study medications will be stored in a secure, controlled-access location at the study site.

Study medications will be stored and handled at the clinical site in accordance with instructions in the Pharmacy Manual. Study medications will be stored at controlled room temperature (15-25°C) with excursions up to 30°C for not longer than 48 hours (continuous). The Sponsor must be notified immediately of any temperature excursions or damage to study medications.

Temperature monitoring is required at the storage location to ensure that the study medications are maintained within an established temperature range. The Investigator(s) is responsible for ensuring that the temperature is monitored throughout the total duration of the trial and that records are maintained; the temperature should be monitored continuously by using either in house validated data acquisition system, a mechanical recording device, such as a calibrated chart recorder, or by manual means, such that minimum and maximum thermometric values over a specific time period can be recorded and retrieved as required.

7.2.5. Accountability and Disposition of Study Medication

The Investigator is responsible for maintaining accurate study medication accountability records throughout the clinical trial. The site will be provided with study medication Accountability Logs on which the designated site staff, will record the receipt, dates, quantity, dispensing and return of study medication, as well as any destruction of study medication or return to the Sponsor. Where more than one secure area is being used for storage at a site, all movement of study medication through the Chain of Custody must be recorded in accountability records such that full reconciliation may be completed at the end of the study. The site may use its own study medication Accountability Logs and standard operating procedures, provided the information outlined above is collected.

After completion of the clinical trial, the Investigator is responsible for the disposal or return to the Sponsor or designee. When the Sponsor has indicated in writing that study medication is to be destroyed on site, destruction must be in accordance with local regulations for the product type and a destruction certificate must be provided to the Sponsor.

8. STATISTICAL CONSIDERATIONS

Details of statistical parameters and methods to be used will be described in a Statistical Analysis Plan (SAP). The SAP will be developed and finalized prior to database lock. The SAP will describe the statistical methodology to assess differences between treatment groups, all data handling procedures and definitions, including the methods for managing missing data.

8.1. Sample Size

A total of approximately 40 subjects is planned in this crossover study, with approximately 20 subjects with RBD+PD or MCI in Cohort A, and approximately 20 subjects with LDB or PDD in Cohort B. The sample size for the study parts are based on practical considerations. No formal hypothesis testing is planned.

The crossover design allows for an increased level of precision in estimates as compared to a parallel design with the same number of subjects. For primary and cognition related secondary endpoints, a sample size of 20 subjects in each cohort provides at least 80% power in this cross-

over design to detect a treatment difference of $0.79 \times \text{SD}$ (active versus placebo) or larger for each endpoint of interest, where SD represents the standard deviation for the endpoint of interest.

For cognition related secondary endpoints, a sample size of 40 subjects overall (both cohorts combined) provides at least 80% power in this cross-over design to detect a treatment difference of $0.54 \times \text{SD}$ (active versus placebo) or larger for each endpoint of interest. Sample size assumptions were based on a 2-sided t-test with a Type 1 error rate of 5%, equal (or no) carryover effects, and a correlation of at least 0.3 between study periods. No adjustments were made for dropouts or multiplicity.

8.2. Analysis Populations

The analysis populations are as follows:

Intent to Treat Set (ITT): All subjects who have signed informed consent and have been randomized to a treatment sequence. Subjects will be analyzed according to the treatment sequence assigned at randomization. The ITT will be the analysis set for disposition and select baseline characteristic analyses.

Safety Set: All subjects who received at least 1 dose of study drug (CST103/CST107 or placebo). Subjects will be reported based on treatment and dose received. The Safety Set will be used for reporting of safety analyses.

Full Analysis Set (FAS): All randomized subjects who have taken at least 1 dose of blinded study drug (CST-103/CST-107 or Placebo). Subjects will be analyzed according to the treatment assigned at randomization. The Full Analysis Set will be used for evaluating the pharmacodynamic endpoints, and selected secondary endpoints.

Per-Protocol Set (PPS): A subset of the Full Analysis Set who sufficiently complied with the protocol. Details of the evaluability criteria will be determined prior to study unblinding and specified in the SAP. The Per Protocol Set may be used for selected safety analyses.

Pharmacokinetic Set (PKS): All subjects in the Safety Set who have at least one valid plasma concentration assessment for CST-103 or CST-107. Subjects will be analyzed according to the treatment received. The PKS will be the analysis set for PK concentration and PK parameter analyses.

Additional analysis populations may be defined in the Statistical Analysis Plan.

8.3. Timing of Analyses

8.3.1. Safety Reviews

Cumulative, blinded safety data from the raw database will be reviewed by the SRM throughout the study when 25%, 50%, and 75% of the subjects are completed. During the review at 50% of subjects completed, primary endpoint data and selected secondary endpoint may be assessed.

8.3.2. Interim Analysis and Accruing Data Review

No formal interim analysis is planned. Accruing data will be evaluated informally on an ongoing basis.

8.3.3. Final Analysis

The final analysis will be performed after the last participant completes their follow-up visit or their last scheduled assessment per the Schedule of Events, or the sponsor terminates the study for any reason.

8.4. Multiplicity

This study is descriptive in nature and informal testing of multiple endpoints may be performed. Given the exploratory nature of the comparisons, no adjustment of Type I error is planned.

8.5. Statistical Methods

Statistical analyses will be performed using SAS 9.3 or higher. Continuous data will display number of subjects, means, standard deviations, median, minimum, and maximum. Categorical data will display frequency counts and percentages. As this study is descriptive in nature, no formal hypothesis testing will be performed. Unless specified otherwise, confidence intervals will be displayed at the two-sided 95% confidence level.

Summaries of disposition and baseline data will be summarized by cohort (A or B), disease criteria within cohort (RBD+PD or MCI for Cohort A, and PDD or DLB for Cohort B), treatment sequence and overall. Summaries of safety, pharmacodynamics, and PK will be presented by disease criteria, treatment (CST103/CST107 versus placebo) and overall. A limited subset of summaries may be presented by treatment sequence and/or period and overall.

For analysis purposes, Baseline will be defined as either the pre-dose measurement taken within each of the study periods, or as the last measurement before the first dose received. This will be detailed in the SAP for each parameter. All data will be listed.

Any changes in the planned analysis will be described and documented in the SAP and/or clinical study report.

8.5.1. Subject Disposition

Subject disposition will be summarized by cohort, disease criteria, treatment sequence and overall using the ITT. Summaries will include the number and percent of subjects: in each analysis population, entering the treatment period, completing each period, completing the study, and discontinuing study prematurely, including a description of the reason for early withdrawal. All data will be listed.

8.6. Subject Characteristics

Demographic and other baseline characteristics will be summarized by cohort, disease criteria, treatment sequence and overall using the ITT. Select summaries may also be repeated in the FAS and Safety Set, if the Safety Set differs from the FAS. All data will be listed.

8.7. Analysis of Primary Endpoints

Primary endpoint data will be summarized by cohort, disease criteria, treatment, and overall across disease criteria (i.e., Overall CST103/CST107 and Overall Placebo) using the FAS. Selected summaries may be repeated in the PPS. All data will be listed.

Informal differences between CST103/CST107 and placebo may be assessed for primary endpoints. For continuous endpoints, the difference is defined as CST107/CST107 minus placebo. Comparisons may be made using a mixed model with factors for disease criteria, treatment, treatment sequence, subject nested in sequence (as a random effect), period, and baseline values as appropriate. Comparisons between treatments may also be compared using the paired t-test and/or nonparametric tests where appropriate.

Additional analyses may be performed and will be described in the SAP.

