8.8. Analysis of Secondary Endpoints

Secondary endpoints related to cognition, physiological symptoms, pupillary data, mood and sleep will be summarized by disease criteria, treatment and overall using the FAS. Select summaries may be repeated in the PPS. Comparisons between treatments will be performed similar to the analysis of primary endpoints. All data will be listed.

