#### 4.3. Sample Size Considerations

A total of approximately 40 subjects is planned in this crossover study. The sample size for the study parts are based on practical considerations. No formal hypothesis testing is planned.

The crossover design allows for an increased level of precision in estimates as compared to a parallel design with the same number of subjects. For primary and cognition related secondary endpoints, a sample size of 20 subjects in each cohort provides at least 80% power in this cross-over design to detect a treatment difference of  $0.79*SD$  (active versus placebo) or larger for each endpoint of interest, where SD represents the standard deviation for the endpoint of interest.

For cognition related secondary endpoints, a sample size of 40 subjects overall (both cohorts combined) provides at least 80% power in this cross-over design to detect a treatment difference of  $0.54*SD$  (active versus placebo) or larger for each endpoint of interest. Sample size assumptions were based on a 2-sided t-test with a Type I error rate of 5%, equal (or no) carryover effects, and a correlation of at least 0.3 between study periods. No adjustments were made for dropouts or multiplicity.

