### 8.1. Primary Endpoint and Analyses

#### Cohort A

Analyses of FERT data will be summarized in a separate analysis plan.

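### Protocol 8.7 leaves open a paired t-test or unspecified nonparametric test that ignores period, beside a mixed model that adjusts for it; the exposure is essentially the Cohort A FERT analysis

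*Protocol*

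**What the plan says.** Protocol 8.7, Analysis of Primary Endpoints, describes informal treatment comparisons. The method named first adjusts for period: "Comparisons may be made using a mixed model with factors for disease criteria, treatment, treatment sequence, subject nested in sequence (as a random effect), period", with baseline as appropriate. The next sentence adds an alternative: "Comparisons between treatments may also be compared using the paired t-test and/or nonparametric tests where appropriate". The synopsis repeats both sentences. Neither place says when the alternative applies, which nonparametric test is meant, or which result stands if the methods disagree. Protocol 8.8 extends the approach to the secondary endpoints: "Comparisons between treatments will be performed similar to the analysis of primary endpoints".

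The SAP does not repeat the paired t-test. Every treatment-comparison model in SAP 8.2 (CANTAB, verbal fluency, BioStamp, ESS, pupillary parameters, GDS, HADS) contains sequence and period. SAP 8.1 restricts Cohort B primary data to listings. For the Cohort A primary endpoint it says: "Analyses of FERT data will be summarized in a separate analysis plan". Waking EEG is deferred in the same way. Neither of those plans is among the documents.

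**The concern.** In a two-period crossover, the active-minus-placebo difference contains the period effect with one sign in one sequence and the opposite sign in the other. A paired t-test or signed-rank test pools these differences without regard to sequence. The period effect then either fails to cancel, which gives bias, or cancels in the mean but stays in the variance, which costs power.

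A period effect is plausible for FERT. The task is given three times per period, six times in all, and the Lead-In familiarisation covers only CANTAB and verbal fluency. FERT is the Cohort A primary endpoint, and Protocol 8.7 is the only supplied text on how it may be tested. In a small signal-seeking study, an unadjusted test could blur or shift the estimate on which the informal reading rests. An open choice between two methods also allows the choice to be made after the results are known.

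**Working it through.** **Inputs from the documents.** Protocol 8.1 and SAP 4.3: two-sided 5% t-test, "a correlation of at least 0.3 between study periods", and "a sample size of 20 subjects in each cohort provides at least 80% power" for 0.79 SD; no allowance for dropout. Protocol 7.2.1: "Eligible subjects will be randomly assigned in a 1:1 ratio to one of the following two treatment sequences", stratified by disease criteria and sex, with no block size stated. In Cohort A that makes four strata (RBD+PD or MCI, by sex).

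**Assumed.** The period effect π (Period 2 minus Period 1) is not given; 0 to 1.0 SD is shown. Dropout rates are also assumed.

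**Step 1: reproduce the plan's power.** The SD of a within-subject difference is √(2 × (1 − 0.3)) = 1.183 SD. With N = 20 and 0.79 SD, the noncentral t gives 80.8% for the paired t (19 df) and 80.6% for the period-adjusted crossover t (18 df). With N = 40 and 0.54 SD it gives 80.4% and 80.3%. Both agree with the stated figure of at least 80%.

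**Step 2: what each method estimates.** With treatment effect τ, the expected active-minus-placebo difference is τ − π for active-first subjects and τ + π for placebo-first subjects. The paired mean therefore estimates

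τ + π × (n placebo-first − n active-first) / N.

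The period-adjusted estimate is half the difference between the sequences in mean Period 1 minus Period 2. It estimates ((τ − π) − (−τ − π)) / 2 = τ, whatever the sequence sizes.

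**Step 3: equal sequences, 10:10.** The bias is zero, but the variance that the paired t-test uses has expectation 1.4 + π² × 20/19 instead of 1.4.
- π = 0.25: √(1.466/1.4) = 1.02, so the standard error is 2% too large.
- π = 0.5: √(1.663/1.4) = 1.09, 9% too large.
- π = 1.0: √(2.453/1.4) = 1.32, 32% too large.

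**Step 4: simulated power at τ = 0.79 SD** (100,000 runs per case).

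| Active-first : placebo-first | π (SD) | Bias, paired (SD) | Power, paired t | Power, period-adjusted |
|---|---|---|---|---|
| 10:10 | 0 | 0 | 81% | 81% |
| 10:10 | 0.25 | 0 | 80% | 81% |
| 10:10 | 0.5 | 0 | 75% | 81% |
| 10:10 | 1.0 | 0 | 59% | 80% |
| 12:8 | 0 | 0 | 81% | 79% |
| 12:8 | 0.5 | −0.10 | 63% | 79% |
| 8:12 | 0.5 | +0.10 | 85% | 79% |

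At 12:8 the bias is 0.5 × (8 − 12)/20 = −0.10 SD, or 0.10/0.79 = 13% of the target difference. Coverage of the paired 95% interval is still about 95% at 12:8 and at 8:12 with π = 0.5, because the inflated standard error offsets the bias. The signed-rank test behaves like the paired t: at 10:10 its power is 79%, 73% and 54% for π = 0, 0.5 and 1.0.

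**Step 5: how much imbalance to expect.** Starting from 10:10 with independent 10% dropout, completer numbers are unequal in about 69% of trials, differ by 2 or more in about 24%, and by 4 or more in about 1%. With 20% dropout, a difference of 4 or more occurs in about 5%. Incomplete randomisation blocks would add to this.

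**The case against.** The strongest reply is that the plan already contains the right method. Protocol 8.7 names the period-adjusted model first, the paired t-test is only permitted, and every SAP model that compares treatments fits period. This stands for all endpoints that the SAP covers. It does not close the point for FERT, because both options in 8.7 are permissive and the plan that chooses between them is not supplied.

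Second, the size of π is unknown. At 0.25 SD with equal sequences the loss is about one point of power. The endpoint is negative emotional bias, and practice that improves recognition need not shift bias. FERT also has a pre-dose session in each period, so change from a period-specific baseline could remove part of a level shift. All of this stands; the simulations ignore baseline. Protocol 8.5 leaves the choice of baseline open, and change from a single pre-study baseline would remove none of the shift.

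Third, SAP 2.1 expects most subjects in Cohort A. The FERT analysis may therefore have more than 20 subjects and a smaller proportional imbalance.

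Three stronger readings are tempting, and the documents do not support them. A reader might infer that all primary and secondary comparisons are exposed, but the SAP models and the Cohort B listings rule that out. A reader might infer that false positives rise and coverage fails whenever the sequences are unequal. At 12:8 with π = 0.5 SD neither happens: type I error is about 4.7%. Appreciable inflation needs larger imbalance, such as 6.4% at 7:13, and dropout alone is unlikely to produce that. A reader might also infer that the paired test always loses power; at 8:12 the bias happens to raise it. Nor do the documents show that the FERT plan uses a paired t-test.

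**Conclusion.** The concern holds as a minor point about an open choice of method. A paired t-test or signed-rank test would be inferior to the period-adjusted comparison if FERT has a period effect of about 0.5 SD or more. It would then cost 5 to 22 points of power with equal sequences. With a 12:8 split and π = 0.5 SD it would move the estimate by 0.10 SD in a direction set by which sequence is larger. With no period effect it does no harm and is marginally more powerful.

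These figures rest on 20 complete pairs, correlation 0.3, a true effect of 0.79 SD, an assumed π, and no baseline adjustment. The live exposure is FERT, plus EEG if its plan tests anything. The weight is limited because no formal hypothesis testing is planned and the option is permissive.

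**What to change.** In Protocol 8.7, the synopsis and the separate FERT plan (and the EEG plan, if it compares treatments):
- State that the mixed model with period and sequence is the governing comparison. It also keeps the disease and baseline terms, which a simple two-sample test would omit.
- Delete the paired t-test, or replace it with the two-sample t-test that compares within-subject Period 1 minus Period 2 differences between the sequences, with the difference in means halved.
- Specify the nonparametric option as the Wilcoxon rank-sum test on the same period differences.

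This is a wording change and needs no new data. It costs one degree of freedom, and about 2 points of power at 12:8 (79% against 81%) if there is no period effect.
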